## 7.2. Treatment Compliance and Modifications

Over the course of active treatment, each patient receiving topiramate will record the total daily dose taken in the eDiary system. If a patient skips a dose(s) or fails to take the specific maintenance dosing regimen, the patient will still be able to continue in the study.

Topiramate treatment compliance will be calculated based on the e-dairy data and if necessary, corresponding pill counts (number of pills actually taken, number of pills retrieved/returned, and the number of pills expected to have been taken by the patient while in the topiramate arm of the study). The overall topiramate compliance rate will be calculated by dividing the total mg of topiramate taken after Week 12 visit by the total mg of topiramate prescribed for all visits after Week 12 visit based upon the duration in the study and then multiplying by 100. The total mg of topiramate prescribed will be based on the maintenance dose set during the Week 12 visit.

The BOTOX compliance rate per visit will be calculated by choosing the minimum of the total units of BOTOX received at a visit divided by 155 U, the total number of injections sites divided by 31, 0.90 if a patient is +/- 8 to 10 days from the visit schedule or 0.80 if a patient is +/- 11 to 14 days from the visit schedule. This minimum value will then be multiplied by 100%. A patient that is 15 or more days from the visit schedule will result in a 0% for compliance (Table 3). The visit schedule is Day 1, Day 84 and Day 168. Overall BOTOX compliance will be the average of the total compliance from each visit.

**Table 3: BOTOX Compliance Formula**

Time to Next BOTOX Injection	BOTOX Compliance Formula
+/- 7 days from the visit schedule	$\text{Min} \left( \frac{\text{Units Injected}}{155 \text{ U}}, \frac{\text{Sites Injected}}{31 \text{ Sites}} \right) * 100\%$
+/- 8 to 10 days from the visit schedule	$\text{Min} \left( \frac{\text{Units Injected}}{155 \text{ U}}, \frac{\text{Sites Injected}}{31 \text{ Sites}}, 0.90 \right) * 100\%$
+/- 11 to 14 days from the visit schedule	$\text{Min} \left( \frac{\text{Units Injected}}{155 \text{ U}}, \frac{\text{Sites Injected}}{31 \text{ Sites}}, 0.80 \right) * 100\%$

+/- 15 or more days from the visit schedule	0%
---	----

For both the BOTOX and topiramate treatment arms, the number and percentage of patients in each compliance rate category (<80%, 80% – 100%, 100% – 120% and >120% as well as <80% and ≥80%) will be reported. If the treatment compliance is less than 80% or greater than 120% and treatment discontinuation is reported at the subsequent office visit, then date of last treatment taken/received from either the eCRF or the eDiary will be the reported as date of discontinuation. Percentages will be calculated from the number of patients who have received treatment in the study period.

If a patient discontinues topiramate treatment, the eCRF for treatment discontinuation must be completed to document the reason for discontinuation. The patient should not be exited from the study, because BOTOX must be administered at the next scheduled office visit (ie, Week 12, 24, or 36).

If a patient discontinues BOTOX treatment, the eCRF for treatment discontinuation must be completed to document the reason for discontinuation and the patient will be exited from the study.

Treatment compliance will be summarized for the Safety Set. Patients will be counted in the treatment arm in which treatment was received. The study drug compliance rate will be summarized using descriptive statistics. Counts and percentage of patients in each compliance rate category will be provided. Denominators for percentages will be the total number of patients who received treatment in each treatment arm and overall.

BOTOX treatment administration by visit, topiramate drug accountability, and topiramate drug accountability per eDiary will be presented in data listings.

## 8. Efficacy Analyses

All efficacy analyses will be conducted by grouping patients according to the treatment they were randomized to receive. The primary and secondary efficacy endpoints will be analyzed on the ITT Set. These analyses will be repeated for the ssITT and PP analysis sets. The primary indicator of efficacy for this study is the analyses on the ITT Set. The analyses for the ssITT and PP Sets will be considered supportive.

Family-wise error rate will be controlled using a hierarchical testing gatekeeping procedure. The testing will begin with the primary efficacy endpoint and continue with the first secondary endpoint in the ranking order, followed by the next, and so on, in a sequential fashion. If the test of the primary endpoint shows statistical significance at the 0.05 level (2-sided), then there is justification to proceed to test the next endpoint in the ranking order; this stepwise process continues for all the endpoints listed in the hierarchical order. However, if no statistical

significance is shown at the 0.05 level (2-sided) for the test of any specified endpoint in the hierarchical order, then that endpoint and all subsequent endpoints below this in the ranking order should be not be considered as an indicator of efficacy, but rather should be considered supportive, regardless of their nominal p-value.

For efficacy analyses, patients who discontinue topiramate and then receive BOTOX will be considered nonresponders and baseline data will be used for the remaining study days for the primary and secondary efficacy endpoints.

All efficacy data will be provided in data listings.

### **8.1. Primary Efficacy Endpoint**

The primary efficacy measure is the proportion of patients with a  $\geq 50\%$  decrease from baseline in the frequency of headache days.

A headache day will be defined as a calendar day (00:00 to 23:59) with 4 or more hours of headache and/or headache of any duration with the use of migraine-specific acute headache medication(s) (ie, ergot alkaloids, ergot combinations, opioids, triptans, or combination analgesics [simple analgesics combined with opioids or barbiturate with or without caffeine]). This variable is derived from the eDiary reports of total duration of all headaches for a given day. It is based on the count of days with at least 4 hours total duration of headaches and/or headache of any duration with the use of migraine-specific acute headache medication(s). The primary timepoint is Week 32, encompassing the last 28-day period ending with Week 32 (ie, Day 198 to Day 225, inclusive, following the Day 1 office visit).

#### **8.1.1. Primary Analysis**

##### *Missing data*

If there are at least 20 days for which the patient has reported headache data (for either headache days or headache-free days), but less than 28 days in a diary period, the data for counts will be prorated accordingly and rounded to the nearest whole number. The prorating will be based on the number of days with reported data in that period.

For example, if there are 24 days with reported data in a 28-day diary window, the headache day count will be multiplied by  $28/24$  and rounded to a whole number. If the patient reported total daily headache durations that indicated 16 headache days and 8 headache-free days, the patient's standardized counts after prorating by  $28/24$  would be 19 headache days and 9 headache-free days.

If a patient reports eDiary data for less than 20 days in a 28-day period, the patient's entries for this time period will be set to missing.

A baseline observation carried forward (BLOCF) method will be utilized to impute missing values for the primary analysis. This type of imputation replaces the missing value with the baseline value; thus, if a patient has a missing entry for any reason (eg, discontinuation due to AE, lost to follow-up, lack of efficacy), the baseline value data will be utilized and the patient will be considered a nonresponder. Patients who discontinue BOTOX and patient randomized to topiramate who discontinue treatment and subsequently receive BOTOX will be considered nonresponders for the primary and secondary analyses and thus baseline value data will be utilized.

BLOCF will also be used to impute missing values for the PRO analyses.

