not exceed 100 mg/day ([Topamax[®] US package insert, 2012](#)). At the next scheduled office visit (ie, week 12), the investigator, at his/her discretion, may adjust the topiramate dose (upward or downward) to be within the range of 50 to 100 mg/day; the patient should remain on this dose for the remainder of topiramate treatment in the study. For all patients completing topiramate treatment or those who discontinue from treatment, a dose taper period of up to 2 weeks is recommended. Refer to Section 5.4.2 for further details.

Patients who complete topiramate treatment at week 36 will be exited from the study at week 36. Patients who discontinue topiramate treatment at any time up to or including week 36 will crossover to receive treatment with BOTOX 155 U for the remainder of the study. The first BOTOX treatment will be administered at the next scheduled office visit, and the patient will return every 12 weeks up to and including the week 36 visit to receive BOTOX treatments, with a final exit visit at week 48. BOTOX treatment can be initiated during the topiramate dose tapering period.

All patients receiving BOTOX in the study will be followed for 12 weeks after the last injection.

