6.1.1 Primary Efficacy Measure

The primary efficacy measure is the proportion of patients with a $\geq 50\%$ decrease from baseline in the frequency of headache days.

A headache day will be defined as a calendar day (00:00 to 23:59) with 4 or more hours of headache and/or headache of any duration with the use of migraine-specific acute headache medication(s) (ie, ergot alkaloids, ergot combinations, opioids, triptans, combination analgesics [simple analgesics combined with opioids or barbiturate with or without caffeine]).

A worst case imputation (WCI) method will be utilized to impute missing values for this analysis. This type of imputation replaces the missing value (ie, frequency of headache days during the 28-day run-in period) with the baseline value. Thus, if a patient has a missing responder value at week 32 for any reason (eg, discontinuation due to adverse events, loss to follow-up, lack of efficacy), then the baseline value data will be utilized and the patient will be considered a nonresponder. Patient(s) randomized to topiramate who discontinue treatment and subsequently cross over to BOTOX will be considered nonresponder(s) for the primary and secondary analyses thus baseline value data will be utilized.

[Redacted text block]

[REDACTED]

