7.2.1.1 Imputation for Missing Diary Entries

The primary efficacy endpoint is a dichotomous variable (responder /nonresponder), and a WCI method will be utilized to impute missing values. If a patient has a missing responder value at week 32 for any reason (ie, discontinuation), the patient will be considered as a nonresponder.

Other types of imputation for the analysis of secondary efficacy variables or in sensitivity/supportive analysis of the primary variable will be detailed in the SAP.

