### 3.4. Dose Adjustment/Modifications

Patients randomized to receive topiramate will receive up to 36 weeks of daily treatment. There will be a 4-week titration phase starting on Day 1 (randomization), followed by a dose maintenance phase for the remainder of topiramate treatment. At the Day 1 office visit, patients will receive an initial dose of topiramate 25 mg/day and will be instructed to continue this dose for 1 week. Patients will be instructed that, during the next 3 weeks of the titration phase, the topiramate dose should be increased in weekly increments of 25 mg/day until a dose of 100 mg/day (or a lower maximum tolerated dose) is reached. Upon discussion with the investigator, the patient may also decrease the dose until the topiramate dose is optimized. Starting at Week 2, topiramate will be administered in 2 divided doses (morning and evening dose). Starting at Week 4 (ie, the maintenance phase), a stable topiramate dose of at least 50 mg/day is required. As per the recommended topiramate dose for migraine prophylaxis, the topiramate dose must not exceed 100 mg/day (Topamax® US package insert, 2012). At the next scheduled office visit (ie, Week 12), the investigator, at his/her discretion, may adjust the topiramate dose (upward or downward) to be within the range of 50 to 100 mg/day; the patient should remain on this dose for the remainder of topiramate treatment in the study. For all patients who complete or discontinue from treatment, a dose taper period of up to 2 weeks is recommended.

Patients who discontinue topiramate at any time on or before Week 36 will receive treatment with BOTOX 155 U for the remainder of the study. The first BOTOX treatment will be administered during the office visit, and the patient will return every 12 weeks up to and including the Week 36 visit to receive BOTOX treatments, with a final exit visit at Week 48. BOTOX treatment can be initiated during the topiramate dose tapering period. A patient who discontinues topiramate early will be considered a nonresponder even if they receive BOTOX treatment.

BOTOX treatment is administered by the physician per protocol and according to the [BOTOX® US package insert, 2015](#), thus dose adjustment/modification will not be made. As with a topiramate patient who discontinues treatment, a patient who discontinues BOTOX early will be considered a nonresponder.

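### As worded, the switcher rule in SAP 8.1.1 and protocol 6.1.1 has no time limit, so stopping topiramate after the primary window has closed can turn an observed Week 32 response into nonresponse

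*SAP*

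**What the plan says.** For patients who switch from topiramate to BOTOX, the two operative sections agree. SAP 8.1.1 (Missing data) states of both sets of analyses: "Patients who discontinue BOTOX and patient randomized to topiramate who discontinue treatment and subsequently receive BOTOX will be considered nonresponders for the primary and secondary". Baseline data are then used. Protocol 6.1.1 says that patients who stop topiramate and "cross over to BOTOX will be considered nonresponder(s) for the primary and secondary analyses thus baseline value data will be utilized". Neither sentence carries a date.

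Two other SAP sections word the rule differently. SAP 8 says that switchers "will be considered nonresponders and baseline data will be used for the remaining study days for the primary and secondary efficacy endpoints". SAP 3.4 says: "A patient who discontinues topiramate early will be considered a nonresponder even if they receive BOTOX treatment". It does not define *early*, and it does not require that BOTOX was received.

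Switching is open until Week 36. Protocol 3.3: "Patients who discontinue topiramate treatment at any time up to or including week 36 will crossover to receive treatment with BOTOX 155 U". The same section says: "Patients who complete topiramate treatment at week 36 will be exited from the study at week 36". At the Week 36 visit a topiramate patient may therefore be recorded either as a completer who exits or as someone who discontinues and is injected. Protocol 8.8 gives the switch injection only at the Week 12, 24 or 36 visit.

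For BOTOX stoppers, SAP 3.4 says that "a patient who discontinues BOTOX early will be considered a nonresponder", and SAP 8.1.1 names them too. The protocol reaches them only through missing data (7.2.1.1: "If a patient has a missing responder value at week 32 for any reason").

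**The concern.** A Week 32 endpoint should be settled by what happened up to Week 32. Read literally, SAP 8.1.1 and protocol 6.1.1 let an open-label decision made up to four weeks later replace a fully observed Weeks 29-32 count with the baseline value. The topiramate arm has that decision point at Week 36. The BOTOX arm barely does, because its last session is at Week 24.

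The wording also leaves the derivation open. One programmer could follow SAP 8.1.1 and rescore every switcher. Another could follow SAP 8 and leave the primary window untouched, because no day of it remains after a late switch. The trigger is unclear as well. SAP 8.1.1 requires receipt of BOTOX, while SAP 3.4 requires only early discontinuation. Anyone who stops after the Week 24 visit is first injected at Week 36, so the stop date and the first BOTOX date can fall on opposite sides of the window's end.

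**Working it through.** **Dates**

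- Primary window: Days 198-225 (protocol 7.2, SAP 8.1) or Days 197-224 (SAP Table 2). Each is 28 days long.
- Week 36 target: Day 253 (SAP Table 1). 253 − 225 = 28 and 253 − 224 = 29 days after the window closes.
- HIT-6 is tested at Week 30, target Day 211. 253 − 211 = 42 days before the Week 36 target.
- Protocol 3.1 and 5.7 in places allow switching only before Week 36. A stop in Weeks 33-35 would still fall after the window.

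**A patient with complete diaries and at least a 50% reduction in Weeks 29-32 who stops topiramate in Week 34 and receives BOTOX at Week 36**

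| Section | Week 32 status |
|---|---|
| SAP 8.1.1 | Nonresponder, baseline substituted |
| Protocol 6.1.1 | Nonresponder, baseline substituted |
| SAP 8 | Labelled nonresponder, but baseline applies only to later days, so the observed count stays |
| SAP 3.4 | Depends on what *early* means |
| Protocol 7.2.1.1 | Not affected, because the value is not missing |

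**Sensitivity analyses (SAP 8.1.2).** Fisher's exact test uses the same outcome. The worst-observation and observed-data analyses address periods with fewer than 20 diary days. None of the three clearly lifts the switcher rule.

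**The plan's own sample size.** With 28% v 44%, two-sided 0.05, 90% power and mean rate 0.36:

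- Uncorrected: n = [1.960·√(2·0.36·0.64) + 1.2816·√(0.28·0.72 + 0.44·0.56)]² / 0.16² = 187.05.
- Continuity-corrected: (187.05/4)·[1 + √(1 + 4/(187.05·0.16))]² = 199.35, so 200 per arm and 400 in total, as stated.

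This point does not change that figure.

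**Effect of rescoring.** Let k be the number of topiramate responders rescored because of a late switch. The documents do not give k, so it is shown as a range. Each one moves the arm by 1/200 = 0.5 points. With equal true rates of 28% (0.28 × 200 = 56 expected responders per arm), the topiramate rate becomes 0.28 − k/200. Exact binomial enumeration at n = 200 per arm gives these two-sided rejection rates:

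| k (topiramate only) | Pooled z-test | Unadjusted Wald log odds ratio |
|---|---|---|
| 0 | 5.03% | 4.95% |
| 1 | 5.17% | 5.10% |
| 2 | 5.59% | 5.53% |
| 3 | 6.32% | 6.26% |

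Rescoring 1 in each arm, or 2 in each arm, leaves the pooled z-test at 5.0%.

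**Rough anchor from the studies cited in protocol 7.5.** It assumes that loss is spread evenly over time and that responders stop as often as everyone else. The documents support neither assumption.

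- Topiramate-plus-placebo arm at Week 24: 95 − 82 = 13 without data. 13/95 × 4/24 = 2.28% per four weeks, and 2.28% × 56 = 1.28 responders.
- Pooled phase 3 BOTOX data at Week 32: 688 − 514 = 174 without data. 174/688 × 4/32 = 3.16% per four weeks, and 3.16% × 56 = 1.77 responders.
- Topiramate only: 1.28/200 = 0.64 points, rejection rate 5.25%.
- Both arms: (1.77 − 1.28)/200 = 0.25 points towards topiramate, rejection rate 5.05%.

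**When a conclusion could change (pooled z).** 56 v 73 responders gives p = 0.069, and 54 v 73 gives p = 0.041. At the design rates, 56 v 88 gives p = 0.0009, and rescoring three (53 v 88) gives p = 0.0002.

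**The case against.** The strongest reply is that the SAP already contains a time-limited reading. SAP 8 is the general rule for efficacy and substitutes baseline only for days after the switch. In SAP 8.1.1 the sentence stands under missing data, with baseline substitution as its mechanism. Protocol 7.2.1.1 makes nonresponse depend on a missing Week 32 value. Read together, an observed count can stand. This shows ambiguity and not a plan that plainly overwrites data. It does not remove the problem, because the same SAP 8 sentence labels every switcher a nonresponder without limit and SAP 8.1.1 is the operative rule for the primary analysis.

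A second reply is that failure to complete 36 planned weeks may be a deliberate failure definition. That is legitimate, but the visible text does not say so.

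A third is redaction. SAP 3.2 and a block following the rule in protocol 6.1.1 are blacked out and may hold a cut-off. That limits the point to the visible text.

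A reader might infer three stronger things that the documents do not support:

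- **A material bias against topiramate.** Neither the number nor the net direction of rescored patients is known. Responders have less reason to stop for lack of efficacy, and the anchor applied to both arms points slightly the other way.
- **Two conflicting Week 32 results.** Protocol 7 plans a summary after Week 32, but SAP 1 sets one lock for the primary analysis after Week 36. Protocol 7 also makes the finalized SAP govern, so this risk is slight.
- **A matching problem in the BOTOX arm.** No session remains after Week 24. The SAP 7.2 rule that dates discontinuation by last treatment applies only when compliance is below 80% or above 120%.

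**Conclusion.** The point holds as a minor defect of specification, with medium confidence and on the visible text only. The switcher rule in SAP 8.1.1 and protocol 6.1.1 has no time limit, SAP 8 conflicts with it for patients who stop in Weeks 33-36, and no listed sensitivity analysis clearly resolves the difference.

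The size is not established and may be nil. For 0 to 3 rescored topiramate responders and none in the BOTOX arm, the two-sided rejection rate at equal 28% rates is 5.0% to 6.3%. At the rough anchor it is 5.25% (topiramate only) or 5.05% (both arms). The anchor counts all patients without data, not responders who switch late. Only a borderline result would change, and the 56 v 73 example was chosen to show one. At the design rates the conclusion would not move. Larger values of k would give larger error rates, but nothing in the documents supports them.

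**What to change.** Change the scoring rule only. No treatment, switching or exit rule is affected.

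1. In SAP 8.1.1, state that a discontinuation sets Week 32 status to nonresponder, with baseline substituted, only if its date is on or before the last day of the primary window. Otherwise use the observed, prorated Weeks 29-32 count. Apply the same condition to both arms.
2. For HIT-6, make the cut-off the Week 30 assessment date.
3. Align SAP 8, SAP 3.4 (replacing the undefined *early*) and protocol 6.1.1.
4. Make the discontinuation date the trigger, not the first BOTOX date. Define the topiramate date once, so that the taper of up to two weeks is handled alike for everyone. Protocol 5.4.2.2, 5.7 (taper starts at discontinuation) and 7.2.3.1 (last dose, in the case it describes) must be reconciled for this.
5. Use the single window end day agreed when SAP Table 2 (Day 224) is reconciled with SAP 8.1 (Day 225).
6. Report the rule that any switch by Week 36 counts as failure as a sensitivity analysis.

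The cost is one date condition in the derivation, one date definition per arm and wording changes in four places. The downside is that the topiramate responder rate, and possibly the BOTOX rate, may be slightly higher than under the literal wording.

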#### *Analysis method*

The primary null hypothesis is that BOTOX and topiramate are equally effective, as measured by the proportion of patients with a  $\geq 50\%$  decrease from baseline in the frequency of headache days per 28-day period at Week 32. The alternative hypothesis is that BOTOX has a different effect than topiramate.

The primary comparison between treatment arms will be performed using a logistic regression model, adjusted by the baseline number of headache days as a covariate. The treatment effect will be summarized using an adjusted odds ratio and 95% Wald confidence limits. The p-value from the Wald Chi-square test will also be reported. A 2-sided test with a p-value less than or equal to 0.05 will be considered as statistically significant. All centers will be pooled for this analysis.

The primary analysis will be repeated for the PP and ssITT Sets, if appropriate.

